5.2 Subject Population

Adults, 18-75 years of age, with mild to moderate sensorineural hearing loss.

5.3 Protection of Vulnerable Subjects

No vulnerable patients are planned to be enrolled in this study.

5.4 Inclusion Criteria

An initial telephone or internet screening of interested persons will take place.

- During this remote screening, prospective subjects will provide their age (subject to verification at Visit 1) and answer a Yes/No question as to whether they have trouble hearing in noise. Those answering "No" will not be considered further for enrollment.
- Those answering "Yes" will then be asked to describe their perceived hearing loss on a 4-point scale (no trouble, a little trouble, a lot of trouble, and cannot hear). Prospects answering at the two extremes will not be considered further for this study.
- Those answering "a little trouble" or "a lot of trouble" will be invited to the in-person Screen that immediately precedes hearing aid fittings in Visit 1. To be eligible to participate in this study, an individual must meet all of the following criteria:
 - (1) Mild-to-moderate bilateral sensorineural hearing loss (thresholds from 250 – 8000 Hz with at least one threshold greater than 20 dB HL and thresholds at 500, 1000, 2000 and 4000 Hz less than or equal to 55, 65, 70, and 80 dB HL, respectively);
 - (2) Mix of male and female subjects (aiming for a representative balance);
 - (3) Mix of prior hearing-aid use (aiming for 70-80% persons with no prior hearing aid use);
 - (4) 18-75 years old (aiming for primarily 50-70 years old, with avg. age ~65 years);
 - (5) Able to read and comprehend English; and
 - (6) Patient willing to provide informed consent.

5.5 Exclusion Criteria

An individual who meets any of the following criteria will be excluded from participation in this study:

- (1) Hearing outside of limits noted above; or
- (2) Self-reported ear-related pathology (including chronic severe dizziness or chronic severe tinnitus).

5.6 Concomitant Treatments

No known concomitant treatments exist for this device.

5.7 Enrollment Screening

Screening for eligibility of this study will be made within 28 days prior to the treatment. If a patient who meets the study criteria joins the study, preliminary effectiveness and safety using the Jabra Enhance Plus in the study will be measured.

6.0 RESEARCH STUDY PROCEDURES

6.1 Study Assessments

A description of all assessments being performed are provided within Section 3.0.

6.2 Study Procedures

6.2.1 Pre-Fitting Procedures: After consent, otoscopy, and audiological measurements verifying candidacy for the study, the subject completes Pre-Fitting of the devices. If the subject does not have a compatible iPhone running iOS 14, one will be supplied for use in this study. The investigator will install the app on the subject's smartphone, pair the devices to the smartphone, and select the appropriate earbud size for each ear prior to the PRO-FIT and SELF-FIT procedures. (These aspects of the fitting process for the Jabra Enhance Plus will be evaluated separately in a usability study.)

i. Fitting begins by placing probe-tube microphones in the subject's ear canals and measuring the Real-Ear Unaided Response (REUR) for each ear.

ii. The Jabra Enhance Plus, powered off, will be placed in the subject's ear with medium-sized earbuds and the Real-Ear Occluded Response (REOR) measured.

- If measurable passive attenuation at frequencies above 500 Hz is not seen, a smaller or larger earbud will be selected by the audiologist and REOR will be remeasured.
- This process will be repeated as needed until a good seal is obtained as verified by the REOR.
- The selected earbud size for each ear will be used by the subject during the remainder of the study.

6.2.2 PRO-FIT: The audiologist will use the air-conduction thresholds measured during the initial screening to generate REAR targets for the NAL-NL2 prescriptive procedure.

- i. Targets will be generated for a speech input level of 65 dB SPL.
- ii. Fine-tuning of REAR by the audiologist to match NAL-NL2 targets will be accomplished using custom device-programming software (AlgoLabTest) to program the gain and compression parameters for NAL-NL2.
- iii. The Audioscan Verifit 1 or 2 real-ear measurement system will be used to verify and fine-tune the fit to match targets for this initial fit for speech input level of 65-dB SPL.

- iv. If the subject has immediate sound-quality complaints, the audiologist will fine-tune the fitting to accommodate those complaints (as was done for the predicate device study; Sabin *et al.*, 2020). The range of adjustments to the frequency response will be constrained to the two alternative responses available on the device via the app. This will be the final fit for PRO-FIT to be worn during the wear-time trial.
- v. No additional fine-tuning will be made by the audiologist to the PRO-FIT fitting for the duration of this study, including the field trial. Although such adjustments *may* be common practice, there is little evidence available about the benefits of such adjustments and they are *not* included in national best-practice guidelines for hearing-aid fitting. The validation study of the Bose Hearing Aid (Sabin *et al.*, 2020) allowed additional adjustments by the audiologist to the PRO-FIT condition in that study after a brief wear-time period (M=5.3 days). However, the gain from 500-4000 Hz was not adjusted in 77% of those subjects and another 14% of their subjects required adjustments of only 5 dB at one or more of those frequencies in either ear after this brief wear-time period. In other words, 91% of the time, no or very minor adjustments, within the range of adjustments that will be available to the user during the wear-time trial in this study, occurred. Further, the user will have access to self-adjustment of volume and choice of frequency response tilt as desired during the wearing period.

6.2.3 SELF-FIT A: Once the earbuds have been selected by the audiologist for the subject and are placed in the ear, subjects will complete the first self-fitting process (Section 16.0, Attachment A).

- i. Subjects will open the mobile device screen, launch the app, and select from drop-down menus to indicate age and gender. (These data facilitate the starting point for the fitting process, but the process can still be completed if left blank.)
- ii. Subjects will be presented with step-by-step fitting instructions on their smartphone describing their task during the self-fitting flow (See Section 16.0, Attachment A.).
- iii. Subjects will be presented with the "Heard It" design of the self-fitting procedure, meaning that they will tap the smartphone screen to indicate when a tone is detected.
- iv. The self-fitting flow requires 5 practice tones and 25 test tones per self-fit. This procedure results in settings as determined by the Jabra Enhance Plus software and is referred to as the "initial fit" and is designed to match NAL-NL2 targets. REAG targets and measures will be calculated by subtracting the input signal level in the sound field from the REAR targets and measures. Comparison of REAG and QuickSIN measures among PRO-FIT, SELF-FIT A, and SELF-FIT B in Visit 1 (in-lab) will be made using these saved *initial-fit* settings for SELF-FIT.
- v. The SELF-FIT process continues uninterrupted with user-preferred adjustments of "filters" or frequency-gain responses. These user-driven fine-tuning adjustments are made while streaming a sound file to the devices and comparing filter settings. (See Attachment 4A for details.) When the subject selects the final settings, these

device settings are saved and become the new default settings for when the device is powered on. These settings are referred to as the "final fit" for the SELF-FIT procedure. Measurements made for SELF-FIT A and PRO-FIT at the end of each wear-time crossover field trial will make use of these *final-fit* settings.

- vi. Once the subject has completed the test, the app will indicate that the subject is finished with personalization of the devices and will return to the home screen of the app.

6.2.4 SELF-FIT B: To assess test-retest reliability, subjects will complete the self-fitting procedure a second time (repeat steps for SELF-FIT A above).

6.2.5 Overview of Procedures at Visits 1, 2, and 3

Successive subjects will be assigned to one of these six condition sequences illustrated in Figure 1 with a total of two cycles through the full set of six sequences at each of the three sites. In the end, two subjects will have been tested in each of the six sequences at each site, six per sequence for the entire study, and any effects of order will be equalized across conditions following the counterbalancing illustrated in Figure 1.

The table below summarizes the primary and secondary outcome assessments to be completed during each study visit. For Visits 2 and 3, REAG will also be established but only for potential explanatory purposes and not as an outcome measure.

Visit	Primary Outcome	Secondary Outcome
1	REAG from REAR; initial fit	QuickSIN; initial fit
2	APHAB; final fit	QuickSIN; final fit
3	APHAB; final fit	QuickSIN; final fit

After the final in-lab measures have been completed during Visit 1, 9 subjects at each site will wear the devices with the final-fit SELF-FIT A settings and the other 9 at each site will begin the crossover trial with the final-fit PRO-FIT settings. After the initial 10-to-14-day wear-time trial, the subjects will return to the lab for the measurement of REAG, aided APHAB, and aided QuickSIN during Visit 2. Each subject will then embark on a second 10-to-14-day wear-time period using the devices with the other fitting settings (SELF-FIT A settings if PRO-FIT settings were worn first, and vice versa). Subjects will return after the second 10-to-14-day wear-time period for completion of REAG, aided APHAB and aided QuickSIN measures with this second fitting, during Visit 3.

Subjects will follow the instructions for the "Self-fitting flow" (Section 16.0, Attachment A) to complete SELF-FIT A and SELF-FIT B procedures. After the installation of software on the smartphone, the pairing of the devices to the smartphone, and the physical fit of the devices, no further assistance will be provided to the subject by the professional or research staff until the completion of Visit 1. When Visit 1 has been completed, the subject will be provided with the devices, the charger, the USB-C cable, and a copy of the User's Manual (Attachment A). The research audiologist will answer questions raised by the subject as he or she pages through the manual. Prior to leaving for the first phase of the field trial, the subject will demonstrate to the audiologist that he or she can insert and remove the devices, adjust the

volume with the app, and place the devices in the charger. The audiologist will log any errors made in this verification of basic use and will correct the subject on those errors once, if needed, prior to the subject leaving with the devices.

For the wear-time field trial, subjects will be asked to wear the devices in a variety of listening situations during the trial including while listening to music and while using the telephone. Subjects will be asked to wear their devices a minimum of two hours per day.

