4.0 DESIGN OF RESEARCH STUDY

4.1 Type of Research Study

This study has two components to assess the safety and effectiveness of the Jabra Enhance Plus device in adults with mild to moderate sensorineural hearing loss. The reliability and validity of the self-fitting method are examined in an in-lab session with counter-balanced conditions. A second component, a single-blind counter-balanced cross-over wear-time field trial, further evaluates the validity of the self-fitting method. Three sites are involved in data collection.

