4.2 Controls and Minimization of Bias

The Sponsor, GN Hearing A/S, should avoid improper influence on any parties participating in, or contributing to, the clinical study or the induction thereof. The selection and treatment of subjects and evaluation of study data are potential sources of bias. Methods that are incorporated within the study design to minimize potential bias include, but are not limited to, screening subjects to confirm study eligibility with defined inclusion/exclusion criteria prior to enrollment; maintaining a log of all subjects screened and enrolled for the study, collecting demographics and medical history at baseline to later assess possible characteristics that may influence endpoints; standardizing data collection requirements and study procedures; requiring all study investigators to meet the requirements of 21CFR Part 54 and a Financial Disclosure by Clinical Investigators; using standardized training materials for all study personnel; and conducting regular electronic monitoring to verify adherence to the protocol and source data.

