5.0 STUDY SUBJECTS

5.1 Sample Size Determination

The sample size was powered by the primary outcome measure of the wear-time field trial, the APHAB, as it is the most variable of the outcome measures across all components of this study. When the sample size in each sequence group in the crossover trial is 16 (giving a total sample size of 32), a crossover design will have 80% power to reject the null hypothesis that the SELF-FIT APHAB mean is inferior to the PRO-FIT APHAB mean based on the mean difference, in favor of the alternative hypothesis that the SELF-FIT mean is non-inferior to the PRO-FIT mean, assuming that the expected difference in means is 0, the non-inferiority difference margin is .084 (or 8.4%), the Crossover ANOVA \sqrt{MSE} is 0.115 (or 11.5%) (giving a standard deviation of differences, σ , of 0.163 or 16.3%) and that the test is made at the 2.5% significance level.

The overall design for the in-lab session is a repeated-measures design comparing outcomes for three procedures: SELF-FIT A, SELF-FIT B, PRO-FIT. Given that SELF-FIT A and B are the same procedure repeated two times, this results in three possible procedure sequences: (1) SELF-FIT A, SELF-FIT B, PRO-FIT; (2) SELF-FIT A, PRO-FIT, SELF-FIT B; and (3) PRO-FIT, SELF-FIT A, SELF-FIT B. An equal number of subjects will receive each sequence at each site to ensure full counterbalancing of order. A total of 36 subjects, 18 per site, will be included which meets the minimum of 32 required for sufficient statistical power, achieves the desired counterbalancing, and allows for some subject attrition or missing data.

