6.2.7 QuickSIN

The subject will be seated in a sound-attenuated booth facing a single loudspeaker. All QuickSIN measures, unaided and aided, will be binaural. The QuickSIN test consists of lists of six sentences that will be played from that loudspeaker at a constant level of 65 dB SPL (at location of subject's head using the method of substitution). This speech level was chosen as one approximating a typical conversational level (60-65 dB SPL) and matching the speech input level used for the REAR measures (65 dB SPL). The level of the co-located background four-talker babble increases across the six sentences for signal-to-noise ratios (SNRs) ranging from +25 to 0 dB SNR (in steps of 5 dB). The subject is asked to repeat each sentence. The audiologist scores whether the subject correctly repeated the predetermined key words in each sentence. The resulting score is interpreted as an SNR loss where a value near 0 indicates better hearing and larger values indicate more difficulty listening in noise.

There are 18 lists of the QuickSIN, but McArdle and Wilson (2006) found four of these to be non-equivalent to the others. The remaining 14 lists will be used as follows. Before the first QuickSIN measure at the end of the initial screening (Visit 1), two lists will be presented as practice lists (Lists 4 and 5). For the remaining 12 lists (Lists 1-3, 6, 8-12, 15, 17, 18), two will be assigned to each of the following conditions: unaided (during initial screen; to permit measures of relative benefit), in-lab initial SELF-FIT A, in-lab initial SELF-FIT B, in-lab initial PRO-FIT (the condition order and list pair assigned for each condition will be randomized for each participant), at end of first 10-to-14-day wear period (Visit 2; either final SELF-FIT A or final PRO-FIT), and at end of

final 10-to-14-day wear period (Visit 3; either final PRO-FIT or final SELF-FIT A). Each QuickSIN score will be based on two lists, 60 keywords, and no lists will be repeated for a given subject.

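### Section 6.2.5 cycles successive subjects through the six sequences, and the plan provides neither random generation nor concealment of the wear-time order; a concealed blocked list would keep the same balance.

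*Combined protocol and SAP*

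**What the plan says.** Section 6.2.5 gives the assignment rule: "Successive subjects will be assigned to one of these six condition sequences illustrated in Figure 1 with a total of two cycles" at each of the three sites. It then states the intended result: "two subjects will have been tested in each of the six sequences at each site, six per sequence for the entire study". It relies on this counterbalancing to equalise order effects. Section 4.1 describes the field trial as "a single-blind counter-balanced cross-over wear-time field trial" and does not call it randomised.

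Section 4.2 opens its list with "Methods that are incorporated within the study design to minimize potential bias include". The list covers eligibility screening, logs, standardised procedures, training, financial disclosure and monitoring. It is expressly not exhaustive, but it names neither random allocation nor concealment, and no other section supplies them for the wear-time order.

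Randomisation is mentioned once, in section 6.2.7, in the account of how QuickSIN lists are allotted: "the condition order and list pair assigned for each condition will be randomized for each participant". That remark concerns the in-lab conditions at Visit 1. It does not say which fit is worn first in the field trial.

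The number of subjects per site is inconsistent. Two cycles of six give 12 per site. Section 5.1 says "A total of 36 subjects, 18 per site, will be included", and section 6.2.5 later says "9 subjects at each site will wear the devices with the final-fit SELF-FIT A settings", with another 9 starting on PRO-FIT.

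**The concern.** If sequences are handed out in a known rotation, whoever books and screens subjects can tell which fit the next subject will wear first. The protocol deliberately mixes new and experienced hearing-aid users (section 5.4 aims for 70-80% with no prior use), and these groups may adapt differently over two successive wear periods. Prior use is a recruitment target, so it can be known before Visit 1. Subjects could then be placed in particular slots, deliberately or simply through scheduling.

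Staff who know the order also fine-tune PRO-FIT for sound-quality complaints (section 6.2.2) and answer questions on the manual before the first wear period (section 6.2.5).

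At stake is the APHAB non-inferiority comparison. It is a primary endpoint, and section 8.4 requires every primary endpoint to be met. Equal counts per sequence cancel a period effect only if that effect is the same in both wear-order groups. Random, concealed allocation makes this hold on average; rotation does not.

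**Working it through.** **1. The plan's own figures.** Inputs from section 5.1: margin 0.084, root MSE 0.115, true difference 0, one-sided 2.5%, 16 per sequence group.
- SD of differences = 0.115 × √2 = 0.163, as stated.
- SE = 0.115 × √(2/N), with N − 2 degrees of freedom. By the noncentral t, power is 80.7% at N = 32, which is the smallest even N reaching 80%. The stated sample size reproduces.
- At N = 36, SE = 0.0271 and power is 85.3%.
- Section 6.2.5: 6 sequences × 2 cycles × 3 sites = 36. This also reproduces.

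**2. How a predictable order can cause bias.** Let τ be the SELF-FIT minus PRO-FIT effect, and let π₁ and π₂ be the period effects (period 2 minus period 1) in the SELF-FIT-first and PRO-FIT-first groups.
- The mean within-subject difference is τ − π₁ in the first group and τ + π₂ in the second.
- The crossover estimate is their average: τ + (π₂ − π₁)/2.
- A common period effect cancels. A differing one leaves a bias of half the difference.

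**3. Illustrative size.** Suppose only new users show a learning effect L, and the proportion of new users differs between the groups by d. Then |bias| = 0.5 × d × L. The documents give neither L nor d, so both are assumptions.
- L = 0.05, d = 0.20: bias 0.005, and 0.005/0.084 = 6% of the margin.
- L = 0.10, d = 0.50 (extreme): bias 0.025, or 30% of the margin. With 75% new users, 9 of 36 subjects are experienced, and d reaches 0.50 only if all 9 fall in the same wear order (18/18 against 9/18).

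Effect on the planned test at N = 36 (noncentral t, noncentrality shifted by bias/SE):

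| Bias | False-positive rate at the margin, if bias favours non-inferiority | Power, if bias is against it |
|---|---|---|
| 0 | 2.5% | 85.3% |
| 0.005 | 3.7% | 80.8% |
| 0.025 (extreme) | 14.4% | 56.2% |

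**4. What random blocks would change.** Each permuted block holds every sequence once. I take the six sequences as the three in-lab orders of section 5.1 crossed with two wear orders, so a block has three of each wear order.
- Balance: two blocks per site give 2 per sequence per site, 6 per sequence overall and 18 against 18 by first-worn fit. Three blocks per site give 9 against 9 per site and 3 × 18 = 54 in total. N, degrees of freedom and power are the same as under rotation for the same N.
- Predictability of first-worn fit, for someone who always names the wear order with more places left in the block: with m of each order, expected correct guesses are m + 4^m / (2 × C(2m, m)) − 1/2. For a block of six (m = 3): 3 + 64/40 − 0.5 = 4.1, and 4.1/6 = 68.3%. For one block of 12 (m = 6): 6 + 4096/1848 − 0.5 = 7.72, and 7.72/12 = 64%.
- A fixed, known cycle gives 100%.
- For the full six-level sequence, the rate in a block of six is (1 + 1/2 + 1/3 + 1/4 + 1/5 + 1/6)/6 = 41%. This is not the relevant figure, because the APHAB contrast depends only on which fit is worn first.

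**The case against.** The strongest reply is that the text does not prove a fixed rotation. It does not state the order within a cycle, Figure 1 is not shown in the copy reviewed, and two cycles that each use all six sequences would also describe two permuted blocks. This stands in part. A reader might infer that every allocation is certainly known in advance; the documents do not support that much. They do support a rule based on order of arrival, with no random element or concealment stated for the wear order. If a random list was intended, the protocol needs to say so.

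A second reply is that section 6.2.7 does randomise condition order. That covers the in-lab conditions only. It also conflicts with the fixed, equally used orders of sections 5.1 and 6.2.5, and the three passages must be reconciled.

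Third, the route to bias is narrow. Eligibility rests on numeric hearing thresholds, subjects are their own controls, the field trial is single-blind, and the APHAB is completed by the subject. No motive for steering is evident. The crossover t-test can also be justified by its usual model (additive period effects, independent errors), so it does not depend on randomisation alone. All of this stands and limits the severity.

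Fourth, a moderate imbalance in new users can arise by chance under random allocation too. If 27 of 36 are new and 18 are drawn at random to each wear order, a difference of 20 points or more needs a split of 16/11 or wider, with hypergeometric probability 12%. Across 25 to 29 new users the probability ranges from 9% to 26%. This also stands, but chance imbalance has no systematic direction and is allowed for in the test's error rate. Steered imbalance is not.

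**Conclusion.** The point holds as a cheap improvement to the design. The plan states a weaker assignment method than it needs, and a concealed random list gives the same balance and power. On the ordinary reading, the first-worn fit of the next subject is foreseeable.

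The possible consequence is a bias in the APHAB contrast of unknown size and direction. The illustrative 0.005 rests on an assumed learning effect of 0.05 and an assumed 20-point imbalance. Larger values need extreme cases. A reader might take 30% of the margin as a realistic estimate, but the documents give no learning effect, and a 50-point imbalance requires nearly every experienced user to fall in the same wear order. Nothing here shows that the trial's result would be wrong.

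Random blocks alone do not solve the problem. Staff who can see past allocations would still guess the first-worn fit correctly about 68% of the time with blocks of six. Withholding the sequence until eligibility is confirmed is what prevents steering at enrolment.

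**What to change.** In section 6.2.5, replace assignment by cycling with assignment from a computer-generated, concealed list of randomly permuted blocks of the six sequences within each site. Use two blocks per site if 12 subjects per site is meant, or three if 18 is meant; the site numbers in sections 5.1 and 6.2.5 must be reconciled first. At 12 per site, one random block of 12 gives the same final balance and slightly lower predictability (about 64%).

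Reveal each sequence in REDCap, which the study already uses, only after eligibility is confirmed at Visit 1. State who generates and holds the list, and add the method to section 4.2.

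State whether the in-lab condition order follows the list or is randomised separately, so that sections 5.1, 6.2.5 and 6.2.7 agree. Section 6.5 allows some withdrawn subjects to be replaced, so also state which sequence a replacement receives.

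The cost is preparing and loading one list. Sample size, power and visits do not change.
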